9.2 ALTERNATIVE PRIMARY ENDPOINT

At the conclusion of the study, a *fully blinded* analysis will be performed to assess the extent of missing primary efficacy endpoint data (ie, 6MWD data). If the absence of 6MWD data in the Treatment Period, combined across subjects, treatment periods, and key visits (Baseline and Study Week 12) to be used for the final primary endpoint analysis would likely lead to an underpowered study or yield indeterminate results, an alternative primary endpoint will be used for the final primary endpoint analysis.

The alternative primary efficacy endpoint is defined as the ranked value for 6MWD measured at each study visit (if present and otherwise imputed for death or too ill to walk) or the ranked value for MVPA measured corresponding to each study visit (otherwise). These data are termed the combined 6MWD/MVPA ranks data.

[REDACTED]

[REDACTED]

The following sections present the pre-specified procedures to be followed.

9.2.1 Pre-specified Primary Endpoint Switching Algorithm

At the conclusion of the study, a *blinded* analysis will be performed to assess the extent of missing primary efficacy endpoint data. The Sponsor has estimated the power of this planned study at various sample sizes and determined that the minimum acceptable power (90% for a 2-tailed $\alpha=0.05$) occurs at approximately 88 subjects providing evaluable primary endpoint data. With planned sample size of 136 evaluable subjects, if at least 65% of the 6MWD has been

collected (or otherwise imputed for death or too ill to walk) across subjects, periods, and key visits (Baseline and Week 12), the primary endpoint will remain, as planned, the 6MWD, regardless of actigraphy data.

If the study completes under the Original Crossover Design, the outcome of the analysis will inform a decision to adopt an alternative primary efficacy endpoint of combined 6MWD/MVPA ranks data as follows:

- If data presence $\geq 65\%$ for 6MWD data (Study Weeks 1, 12, 14, and 25), regardless of data presence for actigraphy, the study will use only 6MWD data as the primary efficacy endpoint.
- If data presence $< 65\%$ for 6MWD data (Study Weeks 1, 12, 14, and 25) and the data presence for actigraphy (Study Weeks 1, 12, 14, and 25) is greater than the presence for the 6MWD data, the study will switch and use combined 6MWD/MVPA ranks data as the primary efficacy endpoint.
- In the event that the data presence $< 65\%$ for 6MWD data (Study Weeks 1, 12, 14, and 25) and the data presence for actigraphy (Study Weeks 1, 12, 14, and 25) is equal or lower than the presence for the 6MWD data, the study will use only 6MWD data as the primary efficacy endpoint.

If the study completes under the Contingent Parallel Design, the outcome of the analysis will inform a decision to adopt the alternative primary efficacy endpoint of actigraphy data as follows:

- If data presence $\geq 65\%$ for 6MWD data (Study Weeks 1 and 12), regardless of data presence for actigraphy, the study will use only 6MWD data as the primary efficacy endpoint.
- If data presence $< 65\%$ for 6MWD data (Study Weeks 1 and 12) and the data presence for actigraphy (Study Weeks 1 and 12) is greater than the presence for the 6MWD data, the study will switch and use combined 6MWD/MVPA ranks data as the primary efficacy endpoint.
- In the event that the data presence $< 65\%$ for 6MWD data (Study Weeks 1 and 12) and the data presence for actigraphy (Study Weeks 1 and 12) is equal or lower than the presence for the 6MWD data, the study will use only 6MWD data as the primary efficacy endpoint.

This algorithm intends that the 6MWD is to be used as the primary efficacy endpoint for this study, except in the case where onsite measurements for the 6MWD are not available.

9.2.2 Alternative Primary Endpoint Hypothesis Test

The primary efficacy endpoint of combined 6MWD/MVPA ranks assesses if inhaled treprostinil will increase the combined ranks at Week 12 over placebo in subjects with PH-COPD. The null and alternative hypotheses are:

$$H_0: \mu_1 = \mu_2$$

$$H_a: \mu_1 > \mu_2,$$

where μ_1 and μ_2 are the baseline-adjusted change from baseline in combined 6MWD/MVPA ranks of the inhaled treprostinil and placebo treatments, respectively.

9.2.3 Alternative Primary Efficacy Endpoint Derivation

The alternative primary efficacy analysis will be primarily based on all available measurements of the 6MWD for the FAS, as observed in the study. The precursor data file for the alternative primary efficacy data set will be the data defined in Section 9.1.2 (ie, all available measurements of the 6MWD as observed in the study, with values missing due to death or being too ill to perform 6MWT being imputed as the worst possible score of 0 meter). These data will be transformed into ranks and missing 6MWD data that were otherwise measured for MVPA will be imputed for this analysis data. All other values that are missing and not present in MVPA data will not be imputed. The final data resulting will be the combined 6MWD/MVPA ranks data set.

[REDACTED]

[REDACTED]

[REDACTED]

All data sets will be retained for further use in the sensitivity analyses specified below (see Section 9.2.5).

9.2.4 Alternative Primary Efficacy Analysis

The primary efficacy analysis to be conducted will follow those specified for the planned primary efficacy endpoint (see Section 9.1.3) with the exception that specification of the variable for 6MWD (only) will be replaced with the variable created for the combined 6MWD/MVPA ranks.

The Sponsor considers that the sample size is sufficiently large to rely on asymptotic theory. The combined data will be standardized (allowing the 2 separate data sets to be combined on the same scale), and the standardized ranking is a transformation towards the normal distribution. As such, a mixed model would be appropriate and generally expected to perform better under a rank transformation than an analysis based on raw values. The Sponsor believes this is consistent with published literature on rank analysis of covariance (Quade 1967; Conover 1982; Lawson 1983)

9.2.5 Alternative Primary Endpoint Sensitivity Analyses

The sensitivity analyses to be carried out for the alternative primary endpoint (the combined 6MWD/MVPA ranks) will include those specified in Section 9.1.4. Assessment for the effect of deviations from the study protocol, carryover effect, and the impact of missing data will use the combined 6MWD/MVPA ranks data instead of 6MWD data. With the use of combined

6MWD/MVPA ranks data, sensitivity analyses will be performed to assess underlying clinical meaningfulness of the rank scores, and the relationship between 6MWD and actigraphy measurements (overall activity and MVPA). In addition, sensitivity analyses will be performed with 6MWD rank data (without imputation of MVPA data), MVPA raw data (by itself, without 6MWD data), and MVPA rank data (by itself, without 6MWD), applying the primary endpoint imputation approach and method of analysis. All analyses will be based on the data, as described in Section 9.2.3, unless otherwise noted. These analyses specified in this section are mandatory if the use of the alternative primary endpoint is triggered; otherwise will only be performed at Sponsor's discretion.

9.2.5.1 [REDACTED]

[REDACTED]

- [REDACTED]
- [REDACTED]
- [REDACTED]
- [REDACTED]
- [REDACTED]

[REDACTED]

9.2.5.2 [REDACTED]

[REDACTED]

9.3 KEY SECONDARY EFFICACY MEASURES

The following secondary endpoints will be formally tested (in order) if the primary endpoint analysis is statistically significant. Each will assess if inhaled treprostinil improves the endpoint at Week 12 over placebo in subjects with PH-COPD. Improvement is defined as a decrease in the NT-proBNP plasma concentration, an increase in MVPA, an increase in overall activity, decrease in Borg dyspnea score, and an increase in the rank for the 6MWD and Borg dyspnea composite score. The null and alternative hypotheses are:

$$H_0: \mu_1 = \mu_2$$

$$H_a: \mu_1 < \mu_2 \text{ or } \mu_1 > \mu_2, \text{ dependent on the stated direction above,}$$

where μ_1 and μ_2 are inhaled treprostinil and placebo treatments, respectively.

9.3.1 Actigraphy

Subjects wore the actigraph accelerometer CentrePoint Insight Watch (ActiGraph., Pensacola, FL) on their nondominant wrist from the onset of the low dose inhaled treprostinil run-in period until study termination. Subjects were provided an actigraph at the time of the screening run-in visit to establish their baseline level of activity. They were asked to wear the device continuously throughout the day, including while sleeping. Physical activity levels were continuously monitored throughout the blinded treatment period. Measurements were not viewable by subject via the watch or otherwise. [REDACTED]

[REDACTED]

[REDACTED]

9.3.1.1 Overall Activity

Summary epoch data were further processed by ActiGraph to produce daily summary data of activity. Derived from the epoch data were aggregate measures of total epochs measured in each

day, total sleep minutes (epochs with awake flag = FALSE), total awake minutes (epochs with awake flag = TRUE), total non-wear minutes (epochs with wear flag = FALSE), and total wear minutes (epochs with wear flag = TRUE). [REDACTED]

Physical activities can be characterized into groupings based on their energy expenditures, measured in Metabolic Equivalent of Tasks (METs), as:

Activity Intensity	Example Activities
Sedentary (<100 counts) (<1.5 MET)	
 • Lying • Standing • Computer work
Light (100-1,951 counts) (1.6-3.0 MET)	
 • Washing dishes • Washing windows • Vacuuming
Moderate (1,952-5,724 counts) (3.1-6.0 MET)	
 • Walking • Ascending/ descending stairs • Lawn mowing
Vigorous (>5,724 counts) (>6.0 MET)	
 • Slow/fast running • Intense sports

Each minute of the day can be converted into an activity intensity, allowing the amount of time in sedentary, light, moderate, and vigorous activities to be determined. Nonsedentary activity is a sum of Light, Moderate, and Vigorous activity. Average counts per day provides a direct measure of overall physical activity. MET = metabolic equivalent of task.

Adapted from Nathan 2020

These activity data were further filtered to include only activity when measured during flagged wear epochs. Summary daily data were available to the Sponsor and investigative site staff throughout the study and a final cumulative transfer of summary data to the Sponsor is to occur after database lock.

The secondary endpoint defined for analysis is the percent change in overall activity (ie, minutes spent in non-sedentary activity) during flagged wake epochs and calculated as absolute

change/baseline (eg, change overall activity [minutes]/baseline overall activity [minutes]). Data will be aggregated across the 7-day baseline to produce an average baseline measurement to minimize day to day variability. Similarly, the Weeks 6 and 12 endpoints will be constructed by averaging across the measurements on the study visit day and the measurements for the 6 days prior.

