### 11.5 SUPPLY AND RETURN OF STUDY DRUG AND DEVICES

Study sites will be supplied with a sufficient quantity of study drug to begin enrollment in the study. At each study visit, all study drug previously dispensed to a subject should be returned to the study site, including all used and unused ampoules.

In the event of Sponsor-approved telemedicine visits, study drug and device accessories may be sent to subjects via mail.

Subjects should return all Sponsor-provided devices and any remaining study drug to the study site at the end of the study (withdrawal, discontinuation, termination, or completion).

In the event of Sponsor-approved telemedicine visits, the Sponsor-provided devices and study drug may be returned to the study site via mail.

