7.1 BASELINE

Given the crossover design utilized for this study, Periods 1 and 2 each have a different baseline for efficacy measurements: Period 1: Day 1 and Period 2: Week 14. With the exception of actigraphy measurements, the baseline value will be defined as the non-missing value immediately prior to dosing with study drug for Period 1: Day 1 and Period 2: Week 14. The baseline period for actigraphy measurements will be the last 7 days during the washout period prior to the day of dosing on Day 1 and Week 14. In the event that the washout period is less than 7 days then only the non-dosing days will be used to derive a baseline average.

For safety evaluations, the baseline will be defined as the last evaluation closest, but prior to, the first dose of study drug during the low dose run-in period.

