8.3.2 Baseline Disease Characteristics

Descriptive statistics will be presented overall based on the randomized population for the following disease characteristics collected prior to randomization:

- age of WHO Group 3 PH-COPD diagnosis (date of diagnosis minus date of birth, in years, by quartiles);
- years of PH-COPD (date for the start of low dose run-in minus date of diagnosis, in years, by quartiles);
- baseline (Day 1) 6MWD;
- baseline (Day 1) Borg dyspnea score;
- baseline (Day 1) 6MWD and Borg dyspnea composite score;
- baseline (Days -7 to -1) actigraphy: average minutes of overall activity and MVPA;
- baseline (Day 1) SGRQ score;
- baseline (Day 1) UCSD SOBQ score;
- baseline (Day 1) plasma concentration of NT-proBNP;
- baseline (Screening Visit 1 and Day 1) FEV₁;
- baseline (Screening Visit 1 and Day 1) FEV₁/FVC;
- lowest recorded SpO₂ during baseline (Screening Visit 1 and Day 1) 6MWT;
- baseline (Day 1) PGA: categorical percentages and average scale value for fatigue and shortness of breath;
- baseline (Day 1) DSP;

- supplemental oxygen use and flow rate (in L/min) with 6MWT at baseline (Screening Visit 1 and Day 1);
- At-home spirometry values at baseline (Day 1).

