9.3.1.2 Moderate to Vigorous Physical Activity

The secondary endpoint defined for analysis is the percent change in MVPA (ie, minutes spent in moderate or vigorous activity) during flagged wake epochs and calculated as absolute change/baseline (eg, change MVPA [minutes]/baseline MVPA [minutes]). Data will be aggregated across the 7-day baseline to produce an average baseline measurement to minimize diurnal variability. Similarly, the Weeks 6 and 12 endpoints will be constructed by averaging across the study visit day measurement and the measurements for the 6 days prior.

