12.4.3 General Considerations For Data Analyses

Section 7: If the study design is changed to a parallel design, efficacy and safety summary tables will follow the general format that baseline and post-baseline data will be presented by the assigned treatment group when those data are observed. Treatments will be labeled as "Treprostinil" and "Placebo" to correspond with the assigned treatment group.

Efficacy and safety data collected after study discharge (after Period 1) will not be presented.

Section 7.1: If the study design is changed to a parallel design for this study, only the Period 1 baseline for efficacy measurements will be used. Except for actigraphy measurements, the baseline value will be defined as the non-missing value immediately prior to dosing with study drug for Period 1: Day 1. The baseline period for actigraphy measurements will be the last 7 days during the washout period prior to the day of dosing on Day 1. In the event that the washout period is less than 7 days then only the non-dosing days will be used to derive a baseline average.

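### The actigraphy follow-up window includes the study visit day and the baseline window excludes it, so percent change in MVPA and overall activity compares unlike days

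*SAP*

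**What the plan says.** **Baseline.** SAP 7.1 defines it as "the last 7 days during the washout period prior to the day of dosing on Day 1 and Week 14". SAP 8.3.2 gives the same window in days: "baseline (Days -7 to -1) actigraphy: average minutes of overall activity and MVPA". For the Contingent Parallel Design, SAP 12.4.3 keeps it: "The baseline period for actigraphy measurements will be the last 7 days during the washout period prior to the day of dosing on Day 1".

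**Follow-up.** For overall activity, SAP 9.3.1.1 forms the Week 6 and Week 12 values by "averaging across the measurements on the study visit day and the measurements for the 6 days prior". For MVPA, SAP 9.3.1.2 forms them by "averaging across the study visit day measurement and the measurements for the 6 days prior". Appendix 12.4 states that sections it does not mention stand unchanged. It amends neither 9.3.1.1 nor 9.3.1.2, so the visit day stays in the follow-up window under both designs.

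**Use.** The MVPA endpoint is "percent change in MVPA (ie, minutes spent in moderate or vigorous activity) during flagged wake epochs", and overall activity is also a percent change. Both are tested formally at Week 12 if the primary endpoint succeeds (SAP 9.3, 9.3.1.3.1). Under the alternative primary endpoint (SAP 9.2, 9.2.3), MVPA also stands in for 6MWD at visits where the walk is missing.

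**The concern.** A change score should compare like with like. Protocol 3.3.1.6 intends actigraphy to describe everyday activity at home, and a visit day is not reliably such a day:

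- An onsite follow-up visit includes a walk test (Protocol 3.3.1.4), and SAP 9.3.1.1 lists walking as a moderate activity. The baseline visit has its own walk test, but that day falls outside the baseline window.
- At the final visit the day may be cut short, because "Subjects should return all Sponsor-provided devices and any remaining study drug to the study site at the end of the study" (Protocol 11.5). That visit is Week 25 in the crossover, Week 12 in the parallel design, or early termination.
- At the visit that ends a treatment period, washout or study exit follows (Protocol 3.1, 7.2.1, 7.3.4). The rest of that day may be off drug, and only subjects on active treatment can lose an effect then.
- A telemedicine visit day has no walk test, and the subject is asked to carry on as normal (Protocol 3.3.1.4).

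The same nominal Week 12 value can therefore contain a different kind of day from one subject to another. At stake are the within-arm percent changes, the precision of two formally tested secondary endpoints and, if it is triggered, the consistency of the MVPA values that enter the alternative primary endpoint.

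**Working it through.** **1. Day count.** Protocol Table 3-1 puts the two baseline visits at Days 1 and 92 and the two end-of-period visits at Days 84 and 175.

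| | Baseline window | Follow-up window | Visit day in baseline | Visit day in follow-up |
|---|---|---|---|---|
| Period 1 | Days -7 to -1 | Days 78 to 84 | 0 of 7 | 1 of 7 (Day 84) |
| Period 2 | Days 85 to 91 | Days 169 to 175 | 0 of 7 | 1 of 7 (Day 175) |

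**2. The plan's own figure.** Protocol 10.2 assumes 80% power at two-sided 0.05 with about 90 evaluable subjects, for 6% to 8% in overall activity or 20% to 25% in MVPA. No standard deviation is given, so this cannot be reproduced, only solved backwards.

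- As within-subject differences, SD = d × √90 / (1.960 + 0.842). This gives 20.3% and 27.1% for d = 6% and 8%, and 67.7% and 84.7% for d = 20% and 25%.
- As 45 per arm, SD = d / (2.802 × √(2/45)). This gives 10.2%, 13.5%, 33.9% and 42.3%.

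The power statement itself is not in dispute.

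**3. Within-arm shift.** Let r be visit-day activity divided by ordinary-day activity (assumed). A subject with no true change shows (6 + r)/7 − 1 = (r − 1)/7:

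| r | 0 | 0.5 | 1.5 | 2 |
|---|---|---|---|---|
| Apparent change | −14.3% | −7.1% | +7.1% | +14.3% |

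The case r = 0.5 corresponds to half of the last day lost at device return, if that day still counts.

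**4. The walk test alone.** If all six minutes count as MVPA and displace nothing else, the seven-day mean rises by 6/7 = 0.86 min/day. As a share of baseline MVPA (level assumed; the documents give none):

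| Baseline MVPA, min/day | 5 | 10 | 20 | 30 | 60 |
|---|---|---|---|---|---|
| Shift | +17.1% | +8.6% | +4.3% | +2.9% | +1.4% |

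These are upper figures. Protocol Appendix 15.1 lets subjects rest while the clock runs, and entry needs only 100 m. The shift also varies with the subject's own baseline and is absent at telemedicine visits, which is how it becomes between-subject noise.

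**5. Treatment contrast.** A shift common to both arms drops out. What remains for a true difference e is:

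- The effect acts equally on all seven days: e × (6 + r)/7. With e = 20%, this is 20 × 6.5/7 = 18.6% at r = 0.5 and 20 × 7.5/7 = 21.4% at r = 1.5.
- The visit day carries no treatment effect (r = 1): e × 6/7. This takes 20% to 17.1%, and 6% to 8% down to 5.1% to 6.9%. With the implied SD unchanged, power is Φ(2.802 × 6/7 − 1.960) = Φ(0.44), about 67% instead of 80%. This is a worst case, because drug is given on site that day.

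**6. With matched windows.** Using Days 77 to 83 against −7 to −1, and 168 to 174 against 85 to 91, r does not enter. A subject with no true change shows 0%.

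**The case against.** The strongest reply is that the tested quantity is a blinded, randomised Week 12 contrast, from which a shift common to both arms largely cancels. In the crossover, device return falls on Period 2 or early termination, and the models carry period and sequence (SAP 7.4). In the parallel design both arms return the device at the same visit. The figures also rest on assumptions: the MVPA level, a walk that is moderate throughout, and a midday hand-back. Parts of SAP 9.3.1, 9.3.1.1 and 9.3.1.3 are redacted, and a valid-day rule there might drop a short final day. Extra activity from travel to the site is an inference, not something the documents state.

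Most of this stands, and it rules out three stronger readings that a reader might infer:

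- **That the artefact is as large as the planned effects.** This sets a within-arm shift of +17% or −7% against between-treatment differences of 20% or 6% to 8%. They are different quantities, and step 5 gives the relevant one.
- **That no kind of visit day matches baseline.** A telemedicine day does resemble a baseline day.
- **That MVPA values substituted for missing walks must rank too low.** The ranking method is redacted. The alternative endpoint also applies only if 6MWD presence is below 65% and actigraphy presence is higher (SAP 9.2.1).

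The reply does not remove the mismatch. No visible text reconciles the two windows or gives a reason for the difference. A valid-day rule would not by itself take the walk out of a fully worn visit day. Off-drug hours at the end of a treatment period do not affect both arms equally.

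**Conclusion.** The inconsistency is in the SAP text, for both actigraphy endpoints and both designs. Its main effect is on within-arm percent changes and between-subject noise. Its effect on the Week 12 contrast is modest: a true 20% difference would read as about 17% to 21%, with r assumed between 0.5 and 1.5 or no treatment effect on the visit day. The documents do not allow a firmer figure. Bias beyond that would need visit-day content, telemedicine use or early termination to differ by arm, and nothing in the documents shows that they do. Any effect on the alternative primary endpoint is possible but depends on redacted text. The point does not threaten the trial's conclusions, but it is a definitional flaw in two formally tested endpoints and can be removed at almost no cost.

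**What to change.** In SAP 9.3.1.1 and 9.3.1.2, and for the MVPA values used in 9.2.3, define each follow-up value (Weeks 6 and 12 of each period, that is Study Weeks 6, 12, 19 and 25) as the mean of the seven full days ending the day before the visit, the same rule as baseline. Apply it identically to onsite, telemedicine and early termination visits, and state that it also holds under Appendix 12.4. Specify it before unblinding.

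The cost is a sentence or two of SAP text and the matching derivation code. Activity is recorded daily throughout the study, so nothing new is collected and no visit changes. If the sponsor prefers to keep the present window, the minimum is a sensitivity analysis without the visit day, also specified before unblinding. That would show the size of the problem but leave the main analysis on mismatched windows.
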